#### 7.4.2.1. Proportional Odds Model for COVID-19 9-Point Ordinal Scale

The odds of observing an improvement in the 9-point ordinal scale on Days 15 and 29 will be analyzed using a proportional odds model for the ITT and PP populations. The odds of observing a better category on the ordinal scale (lower number) will be analyzed separately at Days 15 and 29. The model will include treatment group and ARDS severity (severe vs mild/moderate) as fixed covariates and investigational site as a random effect.

As a sensitivity analysis to the proportional odds model, a Cochran-Mantel-Haenszel test for differences in treatment groups for the 9-point ordinal scale at Days 15 and 29, stratifying for ARDS severity, will also be provided.

#### **7.4.2.2. Improvements and Changes in COVID-19 9-Point Ordinal Scale**

The number and percentage of participants with a 1-point improvement at Days 15 and 29 will be tabulated and summarized by treatment group. A logistic regression model will be used to model the probability of such an improvement that includes treatment group and ARDS severity (severe vs mild/moderate) as fixed covariates and investigational site as a random effect. A similar summary will be used for 2-point improvements at Days 15 and 29.

The time from randomization to first 1- (or more) point improvement in the COVID-19 9-point ordinal scale will be derived. Participants who never improve on-study will be censored at their last assessment or Study Day 29, whichever is earlier. A Kaplan-Meier analysis will be used to describe the time to first improvement.

The mean change in the 9-point scale at Days 15 and 29 will be summarized descriptively by treatment group.

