6.1. Inclusion Criteria

Participants are eligible to be included in the study only if all of the following criteria apply:

- 1. Participant must provide informed consent (participant should provide assent if 12-17 years of age, if possible) before any study specific assessment is performed; informed consent may be obtained from a health care proxy where appropriate and/or institutionally approved method of consenting when applicable (verbal consent) as defined in their local consent form.
- 2. Male or female participants aged \geq 12 years.
- 3. Participants with coronavirus (SARS-CoV-2) infection confirmed \leq 3 weeks prior to randomization by any test with local regulatory approval.
- Participants who are currently hospitalized, intubated (orotracheal or nasotracheal), and receiving invasive mechanical ventilation due to COVID-19–associated ARDS. Participants must have confirmed PaO₂/FiO₂ of ≤ 300 mmHg within 6 hours of randomization.
- 5. Participants with lung imaging showing bilateral or diffuse pulmonary infiltrates on chest x-ray or CT scan.

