6.2. Exclusion Criteria

Participants are excluded from the study if any of the following criteria apply:

- 1. Known history of hypersensitivity to any drugs or metabolites of similar chemical classes as ruxolitinib.
- Presence of severely impaired renal function defined by estimated creatinine clearance < 15 mL/min measured or calculated by Cockroft-Gault equation or calculated by the updated bedside Schwartz equation. Participants must not be receiving CRRT or intermittent hemodialysis at screening.
- 3. Suspected active uncontrolled bacterial, fungal, viral, or other infection (besides COVID-19).
- 4. Known active TB infection.
- 5. In the opinion of the investigator, unlikely to survive for > 24 hours from randomization.
- 6. Currently receiving ECMO.
- 7. Participant may not be sharing a ventilator, or coventilating, with any other patient.

8. Participants who are on long-term use of antirejection or immunomodulatory drugs (eg, JAK inhibitors, IL-6/IL-6R/IL-1RA or IL-1β inhibitors).

Note: Participants who are taking tacrolimus, cyclosporine, and mycophenolate mofetil are eligible for study.

- 9. Treatment with anti–IL-6, IL-6R, IL-1RA, IL-1β, or GM-CSF antagonists, or a BTK inhibitor, within 7 days of randomization.
- 10. Treatment with a JAK inhibitor within 30 days of randomization.
- 11. Concurrent participation in any other interventional clinical study or experimental treatment for COVID-19 or ARDS.

Note: Participants on clinical studies evaluating investigational antivirals are allowed.

- 12. ALT or $AST > 5 \times ULN$ detected within 24 hours at screening (according to local laboratory reference ranges).
- 13. Participants who have known evidence of liver cirrhosis (Child-Pugh A to C).
- 14. Active metastatic malignancy within 1 year of screening, unless with medical monitor approval.
- 15. ANC $< 1.0 \times 10^{9}$ /L at screening (according to local laboratory).
- 16. Platelet count $< 50 \times 10^{9}$ /L at screening (according to local laboratory).
- 17. Pregnant or nursing (lactating) women.
- 18. Females of childbearing potential, defined as all women physiologically capable of becoming pregnant, unless they are using highly effective methods of contraception as defined below, throughout the study and for up to 30 days after stopping treatment.

Highly effective contraception methods (Appendix A) include the following:

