## APPENDIX B. COVID-19 9-POINT ORDINAL SCALE

Participant State	Descriptor	Score
Uninfected	No clinical or virological evidence of infection	0
Ambulatory a	No limitation of activities	1
	Limitation of activities	2
Hospitalized Mild Disease	Hospitalized, no oxygen therapy (defined as SpO 2 ≥ 94% on room air)	3
	Oxygen by mask or nasal prongs	4
Hospitalized Severe Disease	Noninvasive ventilation or high-flow oxygen	5
	Intubation and mechanical ventilation	6
	Ventilation + additional organ support – vasopressors, RRT, ECMO	7
Dead	Death	8

a Defined as not in hospital or in hospital and ready for discharge.

Source: [WHO 2020](#).

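### Participants start at score 6 or 7, so a 1-point improvement has two clinical meanings, and no ordinal analysis adjusts or stratifies for the starting score

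*SAP*

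**What the plan says.** Protocol 6.1 admits participants who are "currently hospitalized, intubated (orotracheal or nasotracheal), and receiving invasive mechanical ventilation due to" COVID-19-associated ARDS. On the scale in SAP Appendix B, score 5 is "Noninvasive ventilation or high-flow oxygen", score 6 is "Intubation and mechanical ventilation" and score 7 is "Ventilation + additional organ support – vasopressors, RRT, ECMO". Protocol 6.2 narrows what can produce a 7 at entry. It excludes current ECMO and adds: "Participants must not be receiving CRRT or intermittent hemodialysis at screening".

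SAP 7.4.2.2 defines the responder summary: "The number and percentage of participants with a 1-point improvement at Days 15 and 29 will be tabulated and summarized by treatment group". The accompanying logistic model contains treatment, ARDS severity and a random site effect, and the 2-point endpoint is handled in the same way. Time to the first improvement of 1 point or more is described by Kaplan-Meier. Mean change is descriptive.

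SAP 7.4.2.1 states: "The odds of observing an improvement in the 9-point ordinal scale on Days 15 and 29 will be analyzed using a proportional odds model". It then explains improvement as a better (lower) category, and its model has the same terms. The CMH sensitivity test is stratified by ARDS severity only.

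SAP 6.1.2 summarizes the baseline ordinal score as a baseline characteristic. It is not a randomization stratum (SAP 3.1) or a subgroup (SAP 7.3.2).

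**The concern.** Two participants who are both at score 6 on Day 15, intubated without additional organ support, are classified differently by the 1-point endpoint. The one who started at 7 has improved and the one who started at 6 has not. A reader of the 1-point percentage cannot tell how many responders are still on a ventilator.

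The starting score may also be prognostic. If score-7 starters do worse overall, a chance excess of them in one arm pulls that arm down in the proportional odds model, which uses the raw category. The same excess could raise that arm's 1-point rate. Two secondary analyses could then be pushed in opposite directions for a reason unrelated to treatment. These endpoints are tested at 2-sided 0.05 without multiplicity adjustment (SAP 3.2), in a trial that closed at 211 participants rather than 500 (SAP 3.3).

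**Working it through.** The documents give no power, rate or sample size for any ordinal endpoint, so there is no plan figure to reproduce. The check maps the scale, lists the model terms and sizes the chance imbalance.

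**1. What each transition counts as** (scale from SAP Appendix B)

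| Start | Later score | 1-point | 2-point | Invasively ventilated |
|---|---|---|---|---|
| 6 | 6 | no | no | yes |
| 6 | 5 | yes | no | no |
| 6 | 4 or lower | yes | yes | no |
| 7 | 6 | yes | no | yes |
| 7 | 5 | yes | yes | no |
| 7 | 4 or lower | yes | yes | no |

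Only the 7-to-6 row is a response on the ventilator, and it affects only the 1-point endpoints. Every 2-point responder is off invasive ventilation, although score 5 suffices from 7 and not from 6.

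**2. Where the starting score enters** (SAP 7.4.2.1 and 7.4.2.2)

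| Analysis | Measured from baseline | Adjusted or stratified for baseline score |
|---|---|---|
| Proportional odds model | no | no |
| CMH test | no | no |
| 1-point logistic | yes | no |
| 2-point logistic | yes | no |
| Kaplan-Meier | yes | no |
| Mean change | yes | no (descriptive) |

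ARDS severity is a PaO2/FiO2 category and does not record vasopressor use. By contrast, SAP 7.4.3.2 stratifies each SOFA component by its own baseline score.

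**3. Chance imbalance in the score-7 share**

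If 2:2:1 held, 211/5 = 42.2 on placebo and 2 × 42.2 = 84.4 per ruxolitinib arm, so about 42 v 84. Let s be the share starting at 7. It is not in the documents; 20-50% is assumed.

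SD of the between-arm difference = √[s(1−s)(1/42 + 1/84)]

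- s = 20%: √(0.16 × 0.0357) = 7.6 points. P(difference ≥ 10 points) = 18.0% by exact binomial and 18.6% by normal approximation.
- s = 50%: √(0.25 × 0.0357) = 9.4 points. P = 28.5% exact and 29.0% normal.

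A difference of 15 points or more has exact probability 4.9% and 11.5% respectively.

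**4. Effect on the 1-point rate (illustration)**

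Assume that 40% reach score 5 or lower from either start. Let q be the chance that a score-7 starter is at exactly 6 on the assessment day, assumed 5-30%. The rate is 40% from score 6 and 40% + q from score 7. The pooled rate is 0.40 + sq, and the share of responders still ventilated is sq/(0.40 + sq).

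- s = 20%, q = 5%: pooled 41%; 0.01/0.41 = 2% still ventilated.
- s = 50%, q = 30%: pooled 55%; 0.15/0.55 = 27% still ventilated.

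A 10-point imbalance shifts the arm difference by 0.10 × q = 0.5 to 3.0 points. Near a 45% rate, the standard error of that difference is √(0.45 × 0.55 × 0.0357) = 9.4 points, so the shift is 0.05 to 0.32 standard errors.

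**5. Precision of the 1-point comparison** (risk-difference scale)

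The share of outcome variance explained by starting score is s(1−s)q²/[r(1−r)], where r is the pooled rate. For s = 50%, q = 15% and r = 47.5%, this is 0.25 × 0.0225/0.2494 = 2.3%, which shortens the standard error by about 1%. For q = 30% and r = 55%, it is 0.25 × 0.09/0.2475 = 9.1%, or about 5%.

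**The case against.** Much of this case stands.

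- The extubation question is largely covered already. The 2-point endpoint always means being off the ventilator. The category tables by day and the stacked bar chart (SAP Appendix A) show the percentage at 5 or lower, and ventilator-free days are compared between arms (SAP 7.4.1).
- The proportional odds model and the CMH test use the actual category, so two participants at score 6 are treated alike there. The mixed meaning belongs to the 1-point endpoints.
- SAP 7.1 sets a general rule of using the randomization strata in efficacy analyses, and the ordinal models follow it. The SOFA component analysis is labelled exploratory.
- Kaplan-Meier and mean change carry no stated arm test. Because Protocol 9.3.1 records the worst score of each day, a pause in support within a day does not count. A single recorded day at 6 still does, because no duration is required.

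A reader might also infer three stronger things that the documents do not support. The first is that the starting score is ignored; in fact the improvement and change endpoints are measured from it. The second is that imbalance is probable or biases the tests. A 10-point gap in 18-29% of allocations is not probable, and chance imbalance is part of the sampling error that a randomized comparison already allows for. The third is that score-7 starters must show the higher 1-point rate. If 35% of score-6 starters reach 5 or lower, and score-7 starters have 20% at 5 or lower plus 15% at 6, both rates are 35%.

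What remains is the mixed meaning of the 1-point responder, which persists even with perfect balance, and the omission of a baseline value already in the database.

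**Conclusion.** The point holds as an inexpensive improvement to secondary analyses, not as an error that invalidates them. The two meanings of a 1-point improvement, and the absence of adjustment or stratification for starting score, follow from the text. That everyone starts at 6 or 7 is inferred from eligibility and the scale. At entry, 7 comes essentially from vasopressors; RRT could contribute only if begun after screening.

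The numerical consequences are modest and rest on assumptions: 2:2:1 allocation of the 211, a 20-50% score-7 share, and the illustrative rates above. On those, 2-27% of 1-point responders would still be ventilated, and a 10-point imbalance would move the 1-point difference by at most about a third of a standard error. The precision gain for the 1-point comparison is small. For the proportional odds model it depends on how prognostic the starting score is, which the documents do not show. The mortality primary endpoint is unaffected.

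**What to change.** In SAP 7.4.2.1 and 7.4.2.2:

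- Add baseline ordinal score (6 v 7) as a fixed covariate in the proportional odds model and in the 1- and 2-point logistic models.
- Add it as a stratification factor in the CMH test, alongside ARDS severity.
- Present the 1-point percentages and the time-to-improvement curve by baseline score within treatment group.
- Optionally, add a supportive line for score 5 or lower at Days 15 and 29. The planned category tables already contain this, so it is a convenience.

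The change needs SAP wording and a variable already collected, with no change to conduct, data collection or the primary analysis. The costs are one extra parameter in models of about 126 participants per comparison (42 + 84), smaller CMH strata (four cells instead of two), and odds ratios that become conditional on starting score, which the table notes should say.

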9.3. Efficacy

9.3.1. Clinical Status (9-Point Scale)

Assessment of clinical status using a 9-point ordinal scale (WHO 2020b) will be recorded at baseline on Day 1 and then again once daily every morning (between 7:00 AM and 12:00 PM local time) through Day 29 of the study period. If a participant is discharged from the hospital, the assessment will be made by phone (between 7:00 AM and 12:00 PM local time). Each day, the worst score for the previous day will be recorded (ie, on Day 3, Day 2 score is obtained and recorded as Day 2). The scale is shown in Table 7.

Participant State	Descriptor	Score
Uninfected	No clinical or virological evidence of infection	0
Ambulatory ^a	No limitation of activities	1
	Limitation of activities	2
Hospitalized Mild Disease	Hospitalized, no oxygen therapy (defined as $\text{SpO}_2 \ge 94\%$ on room air)	3
	Oxygen by mask or nasal prongs	4
Hospitalized	Non-invasive ventilation or high-flow oxygen	5
Severe Disease	Intubation and mechanical ventilation	6
	Ventilation + additional organ support – vasopressors, RRT, ECMO	7
Dead	Death	8

 Table 7:
 COVID-19 9-Point Ordinal Clinical Status

^a Defined as not in hospital or in hospital and ready for discharge.

If the participant dies, the date of death will be collected in the eCRF.

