**Table 1: Objectives and Endpoints**

Objectives	Endpoints
Primary	
To evaluate the 28-day mortality rate of ruxolitinib 5 mg BID + SoC therapy and ruxolitinib 15 mg BID + SoC therapy compared with placebo + SoC therapy in participants with COVID-19–associated ARDS who require mechanical ventilation.	Proportion of participants who have died due to any cause through Study Day 29.
Secondary	
To evaluate the efficacy of ruxolitinib 5 mg BID + SoC therapy and ruxolitinib 15 mg BID + SoC therapy compared with placebo + SoC therapy on in-hospital outcomes in participants with COVID-19–associated ARDS who require mechanical ventilation.	At Day 29, the number of ventilator-free days, ICU-free days, oxygen-free days, vasopressor-free days, and hospital-free days will be summarized by treatment group.
To evaluate the efficacy of ruxolitinib 5 mg BID + SoC therapy and ruxolitinib 15 mg BID + SoC therapy compared with placebo + SoC therapy using a 9-point ordinal scale at Study Days 15 and 29 in participants with COVID-19–associated ARDS who require mechanical ventilation.	Ordinal scale: 
 
• Percentage of participants with at least 2-point improvement in clinical status at Day 15 and at Day 29.
 
• Percentage of participants with at least 1-point improvement in clinical status at Day 15 and at Day 29.
 
• Time to improvement from baseline category to earliest 1-point improvement in the ordinal scale.
 
• Percentage of participants in each 9-point ordinal scale category at Day 29.
 
• Mean change in the 9-point ordinal scale from baseline to Days 15 and 29.
 

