### **3.3. Sample Size Considerations**

The primary endpoint of this study is the proportion of participants who die due to any cause through Study Day 29. The primary endpoint will be tested for each ruxolitinib treatment group using a logistic regression model including treatment (ruxolitinib vs placebo) and ARDS severity (severe [ $\text{PaO}_2/\text{FiO}_2 \leq 100$ ] vs mild/moderate [ $\text{PaO}_2/\text{FiO}_2 > 100$  and  $\leq 300$ ]) as fixed covariates and investigational site as a random (intercept) effect. For placebo randomized 2:2:1 (ruxolitinib 5 mg BID:ruxolitinib 15 mg BID:placebo) assuming a 40% mortality rate for ruxolitinib versus 60% for placebo, a sample size for a pairwise comparison of 100 placebo and 200 ruxolitinib participants (with 500 participants total) will achieve approximately 83% power to detect a statistically significant difference with a nominal 1-sided Type I error of 1.436968%.

Estimated power and Type I error for various scenarios, based on a simulation study of 1000 study replications, are provided in [Table 2](#).

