## 7.4. Analysis of the Secondary Efficacy Parameters

### 7.4.1. In-Hospital Outcomes

The number of ventilator-free, ICU-free, oxygen-free, vasopressor-free, and hospital-free calendar days between Study Days 2 and 29 (inclusive) will be derived using the rules as outlined in [Table 4](#). Note that qualifying vasopressor medications (ie, ATC Class C01CA - adrenergic and dopaminergic agents) will be determined through blinded review of concomitant medications, with the list of medications qualifying as vasopressors included as a note to file prior to final database lock.

Outcome-free days between Days 2 and 29 will be summarized descriptively (mean, mean, standard deviation) with treatment-group statistical comparisons performed using a Kruskal-Wallis test. Participants with missing data that do not permit evaluation for all 28 days, but are known to be alive at Day 29, will have each such day treated as not event-free. Participants who die prior to or on Day 29 will have 0 assigned days for each event-free endpoint. Participants for whom Day 29 survival status cannot be ascertained will be missing from the analysis.

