### 7.4.2. COVID-19 9-Point Ordinal Scale

The COVID-19 9-Point Ordinal Scale (see [Appendix B](#)) will be tabulated by study day, ordinal category, and treatment group. Participants with missing values due to death will be imputed to have Category 8 (death). Participants released from the hospital that are lost to follow-up will be considered missing with regards to this endpoint. Missing intermediate days between observations will be imputed to the worst (highest) category from the 2 nonmissing observations.

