### Tables

Table No.	Title	Population	Standard
Baseline and Demographic Characteristics			
1.1 Disposition			
1.1.1	Analysis Populations	ITT	X
1.1.2	Summary of Participant Disposition	ITT	X
1.1.3	Summary of Number of Participants Enrolled by Country and Site	ITT	X
1.1.4	Summary of Protocol Deviations	ITT	X
1.2 Demography and Baseline Characteristics			
1.2.1	Summary of Demographics and Baseline Characteristics	ITT	X
1.3 Baseline Disease Characteristics			
1.3.1	Summary of Baseline Disease Characteristics and History	ITT	
1.4 Prior Medication and Concomitant Medication			
1.4.1	Summary of Prior Medications	ITT	X
1.4.2	Summary of Concomitant Medications	ITT	X
1.5+ Others			
1.5.1	Summary of General Medical History	ITT	X
Efficacy			
2.1 Primary Efficacy			
2.1.1	Summary of 28-Day Mortality Analyzed by Logistic Regression Model	ITT	
2.1.2	Summary of 28-Day Mortality Analyzed by Logistic Regression Model	PP	
2.1.3	Summary of 28-Day Mortality Analyzed by Logistic Regression Model Using Actual PaO 2 /FiO 2 at Randomization	ITT	
2.1.4	Summary of 28-Day Mortality Analyzed by Logistic Regression Model Treating Participants who are Lost to Follow-Up on or Before Day 29 as Deaths	ITT	
2.1.6	Summary of Tipping Point Analysis for 28-Day Mortality	ITT	
2.1.7	Summary of 28-Day Mortality for Participants Assigned Placebo by Treatment Image	ITT	
2.2 Secondary Efficacy			
2.2.1	Summary of Day 29 In-Hospital Outcomes by Treatment Group	ITT	
2.2.2.1	Summary of COVID-19 Ordinal Scale at Day 1, Day 15, and Day 29	ITT	
2.2.2.2.1	Summary of COVID-19 Proportional Odds Model at Day 15 and Day 29	ITT	

Table No.	Title	Population	Standard
2.2.2.2.2	Summary of COVID-19 Proportional Odds Model at Day 15 and Day 29	PP	
2.2.2.3.1	Summary of Participants With a 2-Point Improvement in COVID-19 Ordinal Scale on Day 15 or Day 29	ITT	
2.2.2.3.2	Summary of Participants With a 1-Point Improvement in COVID-19 Ordinal Scale on Day 15 or Day 29	ITT	
2.2.3.4	Kaplan-Meier Analysis of Time From Randomization to First Improvement in COVID-19 Ordinal Scale	ITT	
2.2.4	Summary of Change in COVID-19 Ordinal Scale at Study Day 15 and 29	ITT	
2.2.5	Summary of COVID-19 Ordinal Scale by Study Day	ITT	
2.2.6.1	Summary of Change in SOFA Score at Days 3, 5, 8, 11, 15, 29	ITT	
2.2.6.2	Summary of SOFA Score at Study Days 1, 3, 5, 8, 11, 15, and 29	ITT	

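### Time to first improvement has no rule for deaths; censoring them as the text reads makes the Kaplan-Meier curve overstate improvement

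*SAP*

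**What the plan says.** SAP Table 1 lists this secondary endpoint: "Time to improvement from baseline category to earliest 1-point improvement in the ordinal scale". SAP section 7.4.2.2 measures the time from randomization to the first improvement of at least 1 point. Its only censoring rule is: "Participants who never improve on-study will be censored at their last assessment or Study Day 29, whichever is earlier". Kaplan-Meier is then used descriptively, with no test or model. Protocol section 12.4.1 has the same censoring sentence. The outputs in SAP Appendix A are Table 2.2.3.4 ("Kaplan-Meier Analysis of Time From Randomization to First Improvement in COVID-19 Ordinal Scale") and Figure 4.2.1.

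Four other places bear on the point:

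- Protocol section 9.3.1: clinical status "will be recorded at baseline on Day 1 and then again once daily every morning" through Day 29. On death, it says: "If the participant dies, the date of death will be collected in the eCRF".
- SAP section 7.4.2, the parent section, sets scale values that are missing because of death to Category 8.
- SAP section 7.4.1 gives event-free days an explicit death rule: "Participants who die prior to or on Day 29 will have 0 assigned days for each event-free endpoint".
- SAP section 7.4.3.2 gives SOFA components one too: decedents receive the worst score, 4.

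**The concern.** A participant who dies without improving has never improved, so the censoring sentence applies. With daily scoring, the last assessment made in life falls within about a day of death. Read literally, the rule censors these participants at death.

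Kaplan-Meier assumes that a censored participant has the same future chance of the event as those still under observation. A participant who has died has none. One minus Kaplan-Meier (1-KM) therefore exceeds the proportion who improved whenever such deaths come before later improvements. That direction does not depend on any assumed rate.

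Death is not a rare competing event here, since the trial was planned on 40% to 60% mortality. If survivors improve equally often in both arms, evenly spread events give a larger excess in the arm with more deaths, so a drug that lowers mortality would look less different from placebo than it is. A median could also be reported that was never reached.

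**Working it through.** **Inputs.** Mortality comes from SAP section 3.3: "assuming a 40% mortality rate for ruxolitinib versus 60% for placebo". The documents give no improvement rate, no event timing and no rate of death without improvement, so these are assumptions and are varied below.

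**The plan's own figure.** There is none for this endpoint. The mortality rates come from the power statement of about 83% (100 vs 200 participants, 1-sided alpha 0.01436968). Fisher's exact test gives 83.2% and the continuity-corrected normal approximation 83.7%, so that statement reproduces.

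**Formula.** Let m be mortality, s the share of survivors who improve, and r the share of decedents who improve before death.

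- Truly improved: ci = (1 − m)s + m·r
- Died without improving: cd = m(1 − r)
- Deaths censored at death, with improvements and deaths spread alike over time: 1-KM = 1 − (1 − cd − ci)^(ci/(cd + ci))

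The same expression results from constant hazards. A daily version uses 28 equal steps and censors deaths at the end of the day.

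**Central case, s = 0.7, r = 0.**

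- Placebo: ci = 0.4 × 0.7 = 0.28 and cd = 0.60. 1-KM = 1 − 0.12^(0.28/0.88) = 0.491 (daily 0.478).
- Ruxolitinib: ci = 0.6 × 0.7 = 0.42 and cd = 0.40. 1-KM = 1 − 0.18^(0.42/0.82) = 0.585 (daily 0.578).
- Gap between arms: 0.094 (daily 0.100) against a true 0.42 − 0.28 = 0.14.
- In the daily version the ruxolitinib curve crosses 50% at Day 27, although only 42% improved.

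**Other rates, same timing** (1-KM, daily version in brackets, against truth):

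| s, r | Placebo | Ruxolitinib | Gap |
|---|---|---|---|
| 0.5, 0 | 0.331 (0.324) vs 0.200 | 0.403 (0.399) vs 0.300 | 0.072 (0.075) vs 0.100 |
| 0.9, 0 | 0.701 (0.673) vs 0.360 | 0.801 (0.788) vs 0.540 | 0.100 (0.116) vs 0.180 |
| 0.7, 0.2 | 0.619 (0.608) vs 0.400 | 0.649 (0.643) vs 0.500 | 0.030 (0.035) vs 0.100 |

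**Equal improvement in both arms.** If 30% truly improve in each arm, and 60% (placebo) vs 40% (ruxolitinib) die unimproved, the curves read 1 − 0.10^(0.30/0.90) = 0.536 and 1 − 0.30^(0.30/0.70) = 0.403. That falsely favours placebo.

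**Timing, s = 0.7, r = 0.** The bounds run from no excess (every improvement before every death) to ci/(1 − cd) = 0.70 in both arms (every death first). Two intermediate cases were simulated:

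- Improvements earlier (Beta(1.5, 3) over Days 2-29), deaths even: about 37-38% against 28% on placebo and 51% against 42% on ruxolitinib. The gap is about 13 points against 14.
- Deaths early (Beta(1.5, 3)), improvements mid-period (Beta(2, 2)): about 58-59% and 64%. The gap is about 5 points against 14.

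**Check of the remedy.** In a simulation of 400,000 per arm (central case, even times on Days 2-29), holding decedents at risk to Day 29 gave 0.279 and 0.419 with no median. Censoring them at death gave 0.477 and 0.576.

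**The case against.** The strongest reply is that SAP section 7.4.2.2 sits under section 7.4.2, whose conventions already cover death. Death is a score on the scale, and values missing because of death become Category 8. A decedent could therefore be said to have a value every day to Day 29. On that reading, the Day 29 limit serves participants with complete values and the last-assessment limit serves those lost to follow-up. Decedents stay at risk to Day 29 and the curve is right.

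This reading is possible and may be what was meant. But the convention concerns missing scale values, and nothing says that an imputed score counts as an assessment for censoring. Event-free days and SOFA components each state their death rule at the endpoint, and this endpoint does not. Two programmers could draw different curves from the same data.

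Two further points stand in part:

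- **Size.** It depends on assumptions. A move from 7 to 6 counts as improvement, so some decedents will have improved first. If improvements come early, the distortion of the gap nearly vanishes. Even then, the excess within each arm remains about 9 points in the case above.
- **Reach.** The analysis is descriptive, and the report also shows the ordinal scale by study day and improvement percentages at Days 15 and 29. This limits the consequence but does not correct the curve.

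**Conclusion.** The concern holds. The censoring rule is silent on death, and its literal reading makes the Kaplan-Meier curve overstate improvement. The silence and the direction are firm. Whether the reported curve will be biased depends on which reading the programmer takes, so this is an unresolved rule and not a certain error.

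The size is illustrative. At the planned mortality, with 50% to 90% of survivors and no decedents improving, evenly spread event times and no other censoring, the excess is 12-34 points on placebo and 10-26 on ruxolitinib. Other timings move it between the bounds above.

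The effect is confined to Table 2.2.3.4 and Figure 4.2.1. The primary endpoint, the proportional odds model, the Day 15 and Day 29 improvement percentages, the by-day category tables and event-free days are unaffected. It should be fixed, because a listed secondary endpoint could otherwise be reported with a wrong percentage and a false median.

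**What to change.** Replace the censoring sentence in SAP section 7.4.2.2 with: *Participants who die without prior improvement remain in the risk set and are censored at Study Day 29; participants alive and lost to follow-up without improvement are censored at their last assessment.*

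Alternatively, report the Aalen-Johansen cumulative incidence of first improvement, with death as a competing event. In either case, settle the rule before unblinding, so that it is not chosen after the curves are seen.

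The cost is one sentence and a few lines of code. Date of death is already collected, so no new data are needed. The downside is a lower curve than the literal rule would give, whose median may not be reached.
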